#### 9.6. Source Documents

Source documents provide evidence for the existence of the subject and substantiate the integrity of the data collected. Source documents are filed at the Investigator's site. Source documents include information contained in original records and certified copies of results, observations or other facets required for the reconstruction and evaluation of the study that is contained in source documents. Examples of source documents may include (but are not limited to) hospital records, clinical and office charts, laboratory data/information, subjects' diaries or evaluation checklists, pharmacy dispensing and other records, recorded data from automated instruments, ECGs, X-rays, ultrasounds, right heart catheterization reports, ECHO, and PFTs. Data collected during the study must be recorded on the appropriate source documents.

Data reported on the eCRF or entered in the eCRF that are transcribed from source documents must be consistent with the source documents or the discrepancies must be explained. The Investigator may need to request previous medical records or transfer records, depending on the study. Also, current medical records must be available.

eCRFs must be completed for each subject screened/enrolled in this study. These forms will be used to transmit information collected during the study to the Sponsor and regulatory authorities, as applicable.

The Investigator will document subject data in his/her own subject files. These subject files will serve as source data for the study. All eCRF data required by this protocol will be recorded by investigative site personnel. All data entered into the eCRF will be supported by source documentation.

The Investigator or an authorized member of the Investigator's staff will make any necessary corrections to the eCRF. All changed information, including the date and person performing the corrections, will be available via the audit trail, which will be part of the electronic data capture system. For any correction, a reason for the alteration will be provided. The eCRFs will be reviewed periodically for completeness and acceptability by Sponsor personnel (or their representatives). The Sponsor (or their representatives) will also be allowed access to all source documents pertinent to the study in order to verify eCRF entries. The Investigator will review the eCRFs for completeness and accuracy and provide his or her electronic signature and date to eCRFs as evidence thereof.

The documentation related to the validation of the eCRFs will be maintained in the Trial Master File (TMF). The TMF will be maintained by the Contract Research Organization during the course of the clinical study and by the Sponsor upon completion of the study.

## 9.7. Study and Site Closure

The Sponsor or their designee reserves the right to close the study site or terminate the study at any time for any reason at the sole discretion of the Sponsor. Study sites will be closed after study completion. A study site is considered closed when all required documents and study supplies have been collected and a study-site closure visit has been performed.

The Investigator may initiate study-site closure at any time, provided there is reasonable cause and sufficient notice is given in advance of the intended termination.

Reasons for the early closure of a study site by the Sponsor or Investigator may include, but are not limited to:

- Failure of the Investigator to comply with the protocol, the requirements of the IRB or local health authorities, the Sponsor's procedures, or GCP guidelines
- Inadequate recruitment of subjects by the Investigator
- Discontinuation of further study treatment development

## MODIFICATION HISTORY

Unique Identifier for this Version	Date of the Document Version	Author		Significant Changes from Previous Authorized Version
1.0	15JAN2021		and	Not Applicable – First Version

Document:	\\quintiles.net\enterprise\Apps\sasdata\SASb\SAS\Arena\APD371\FZA87549\Biostatistics\Documentation\SAP\APD371-202_Main_Study_SAP_Final.docx			
Author:	and	Vers Num		1.0
		Vers	ion Date:	15JAN2021
Template No.: CS_TP_BS016 Revision 5			Reference:	CS_WI_BS005
Effective Date: 01Apr2018				

## 1. LIST OF ABBREVIATIONS

Abbreviation	Meaning
AABS	average abdominal bloating score
AADS	average abdominal discomfort score
AAPS	average abdominal pain score
AE	adverse event
ANCOVA	analysis of covariance
APS	abdominal pain score
ATC	Anatomical Therapeutic Chemical
ATC3	Anatomical Therapeutic Chemical: Therapeutic (Level 3)
AUC	area under the curve
BLQ	below the lower limit of quantification
BM	bowel movement
BMI	body mass index
BP	blood pressure
CC	complete cases
CI	confidence interval
CM	concomitant medication
СМН	Cochran-Mantel-Haenszel
CS	clinically significant
CSBM	complete spontaneous bowel movement
CSR	clinical study report
CV	coefficient of variation
DSMB	Data Safety Monitoring Board
ECG	electrocardiograms
eCRF	electronic case report form
EDC	electronic data capture

#### Analysis Plan – Main Study

Page 9 of 77

Abbreviation	Meaning
EQ-5D	European Quality of Life-5
ET	early termination
FAS	Full Analysis Set
HADS	Hospital Anxiety and Depression Scale
HR	heart rate
IBS	irritable bowel syndrome
IBS-C	irritable bowel syndrome with predominant constipation
IBS-D	irritable bowel syndrome with predominant diarrhea
IBS-QoL	Irritable Bowel Syndrome-Quality of Life
IBS-SSS	Irritable Bowel Syndrome-Severity Scoring System
ICF	informed consent form
LS	least-squares
LTE	long-term extension
MAR	missing at random
MCMC	Markov Chain Monte Carlo
MedDRA	Medical Dictionary for Regulatory Activities
MI	multiple imputation
MMRM	mixed-effects model repeated measures
NCS	not clinically significant
NRI	non-responder imputation
OC	observed cases
PCS	Potentially Clinically Significant
PGIC	Patient Global Impression of Change
PK	pharmacokinetic
PROMIS	Patient-Reported Outcomes Measurement Information System
PT	preferred term

#### Analysis Plan – Main Study

Page 10 of 77

Abbreviation	Meaning
SAE	serious adverse event
SAP	Statistical Analysis Plan
SBM	spontaneous bowel movement
SD	standard deviation
SI	International System of Units
SOC	System Organ Class
TEAE	treatment-emergent adverse event
TFL	table, figure, and listing
TID	3 times per day
ULQ	upper limit of quantification
VAS	Visual Analog Scale
VS	vital signs
WHODD	World Health Organization Drug Dictionary
WK	week

#### 2. Introduction

This document describes the rules and conventions to be used in the presentation and analysis of efficacy, safety, and pharmacokinetic (PK) data for the Main Study described in Protocol APD371-202. It describes the data to be summarized and analyzed, including specifics of the statistical methods to be implemented. This statistical analysis plan (SAP) is based on protocol version APD371-202 (Amendment 3, dated 03FEB2020) and focuses on analyses for the Main Study. There will be a separate SAP or an amendment to this SAP for the long-term extension (LTE) part of the study. A separate analysis plan will describe the genetic and biomarker analyses.

The table, figure and listing (TFL) shells are prepared in a separate file based on this analysis plan. Upon approval of the SAP, some updates (including but not limited to titles, footnotes, headings and re-numbering of tables, etc.) on TFL shells are allowed without a SAP amendment as long as the updates within TFL shells do not conflict with the contents of the SAP.

#### 3. STUDY OBJECTIVES

#### 3.1. Primary Objectives

The primary objectives are:

- To compare the efficacy of different doses of olorinab versus placebo on improvement in abdominal pain severity in subjects with irritable bowel syndrome (IBS)
- To compare the safety and tolerability of different doses of olorinab versus placebo in subjects with IBS

#### 3.2. SECONDARY OBJECTIVES

The secondary objectives are:

- To compare the proportion of abdominal pain treatment responders for different doses of olorinab versus placebo
- To compare change in pain frequency for different doses of olorinab versus placebo
- To characterize the pharmacokinetics of olorinab and its predominant metabolites, and its predominant, in subjects with IBS

#### 4. STUDY DESIGN

#### 4.1. GENERAL DESCRIPTION

The Main Study is designed to assess the efficacy, safety, and tolerability of olorinab in the treatment of abdominal pain in subjects with IBS with predominant constipation (IBS-C) or predominant diarrhea (IBS-D) who are not on concomitant treatment for IBS. The study is a Phase 2, multi-center, randomized, double-blind, placebo-controlled, parallel-group study that includes a Screening Period (up to 4 weeks for subjects who consent to colonic biopsy, up to 2 weeks for all other subjects), a Run-in Period (at least 2 weeks; 14-19 days), a randomized Main Study Treatment Period (12 weeks), and a post-treatment Main Study Follow-Up Period (2 weeks), totaling 16-20 weeks (Figure 1). After the Run-in Period, eligible subjects will be equally randomized into 1 of 4 treatment groups (olorinab 10, 25, or 50 mg tid or placebo tid). Randomization will be stratified by sex (male, female) and IBS subtype (IBS-C, IBS-D). The number of subjects enrolled with IBS-C will be approximately equal to the number of subjects enrolled with IBS-D. Subjects will be screened until approximately 60 subjects have been randomized per treatment group for a total of approximately 240 subjects. For subjects randomized under protocol amendment 1, there was an overnight observation period following randomization on Day 1, with orthostatic vital sign (VS) and 12-lead electrocardiogram (ECG) measured at multiple timepoints. Blood samples will be collected for measurement of plasma concentrations of olorinab and its metabolites. Samples will be used to evaluate the PK of olorinab and its predominant metabolites

The PK sampling schemes specified in protocol amendment 1 include the following timepoints:

- Blood samples for the analysis of olorinab and metabolite plasma concentrations will be collected at study visits at Weeks 2 (Visit 4) through 10 (Visit 7) prior to the first daily dose. Blood samples will also be collected at Weeks 12 and 14 during the scheduled study visit. At Week 4 (Visit 5), in addition to samples collected prior to the first daily dose of study treatment, blood samples will be drawn 0.5, 1, and 2 hours after the first daily dose of study treatment. If a subject discontinues the study, a final PK sample will be collected at the Early Termination visit.
- Pharmacokinetic blood samples will be collected on Day 1 prior to and 0.5, 1, 2, 4, and 8 hours after the first dose of study treatment and 10 hours after the first dose of study treatment (2 hours after second dose). Additional samples will be collected on Day 2, prior to the first daily dose of study treatment and 2 and 4 hours after the first daily dose.

The PK sampling schemes specified in protocol amendment 2 and protocol amendment 3 (Main Study) include the following timepoints:

• Pharmacokinetic blood samples will be collected at study visits at Weeks 2 (Visit 4) through 10 (Visit 7) prior to the first daily dose. Blood samples will also be collected at Weeks 12 and 14 during the scheduled study visit. At Week 4 (Visit 5), in addition to samples collected prior to the first daily dose of study treatment, blood samples will be drawn 0.5, 1, and 2 hours after the first daily dose of study treatment administered at the clinic during the study visit. If a subject discontinues the study, a final PK sample will be collected at the Early Termination visit.

Pharmacokinetic blood samples will be collected on Day 1 prior to the administration of study treatment and 0.5, 1, and 2 hours after the administration of study treatment.

[figure not shown]

Figure 1: Schematic Diagram of Main Study Design

Notes: The Screening Period may be extended to up to a total of 4 weeks for subjects who consent to colonic biopsy. The last day of the Run-in Period is Day -1 and the first day of the Main Study Treatment Period is Day 1. There is not a designated Day 0 in this study. For subjects randomized under protocol amendment 1, there was an overnight observation period following randomization on Day 1, with orthostatic vital sign (VS) and 12-lead electrocardiogram (ECG) measured at multiple timepoints. See orthostatic VS and ECG analyses under Safety Section for details.

#### 4.2. SCHEDULE OF EVENTS

Schedule of events can be found in of the protocol.

#### 4.3. CHANGES TO ANALYSIS FROM PROTOCOL

There are no changes in analysis or definitions from those planned in the final protocol and no changes required due to COVID-19.

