# Statistical analysis:

The primary endpoint, change in AAPS from Baseline to Week 12, will be analyzed using a mixed-effects model repeated measures (MMRM) analysis with treatment, stratification factors, visit, and treatment-by-visit interaction as factors and Baseline AAPS as a covariate. Least squares means, standard errors (SEs), and 95% CIs for the treatments and their difference will be presented together with the p-values.

Unless otherwise specified, continuous endpoints will be analyzed using a MMRM analysis with treatment, the stratification factors, visit, and treatment-by-visit interaction as factors and Baseline AAPS and Baseline value (if applicable) as covariates. Least squares means, SEs, and 95% CIs for the treatments and their difference will be presented together with the p-values.

Categorical endpoints will be analyzed by either the Cochran-Mantel-Haenszel method, Fisher's exact test, or by logistic regression with a model that includes treatment and stratification factors as factors and Baseline AAPS and Baseline value (if applicable) as covariates. The odds ratio of each olorinab treatment group relative to placebo and percentage of difference from placebo will be presented together with corresponding 95% CIs and the p-values.

Time-to-event endpoints will be displayed using Kaplan-Meier plots and analyzed with Cox regression with a model that includes treatment and stratification factors as factors and Baseline AAPS and Baseline value (if applicable) as covariates. The hazard ratio will be presented together with 95% CIs and the p-values.

Pairwise comparisons of each olorinab treatment group compared to placebo will be conducted. In addition, analyses of the pooled olorinab treatment groups compared placebo will be conducted.

Where statistical assumptions (eg, proportional hazards, normality, proportional odds) are not met, alternative approaches will be evaluated (eg, non-parametric analysis, log transformation).

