### 8.3. Statistical Analyses

Details regarding the statistical analyses will be provided in the SAPs. The SAP for the Main Study will be finalized prior to database lock (unblinding) of the Main Study and the SAP for the LTE will be finalized prior to database lock for the LTE. Results of the Main Study and the LTE may be reported in 2 separate clinical study reports.

Continuous variables will be summarized using the number of observations, mean, SD, median, minimum, and maximum. Categorical variables will be summarized using frequency counts and percentages. For time-to-event variables, the number of subjects at risk over time, as well as the cumulative percentage of subjects experiencing the event of interest will be presented, based on Kaplan-Meier methodology.

Unless otherwise specified, continuous endpoints will be analyzed using a mixed-effects model repeated measures (MMRM) analysis with treatment, the stratification factors, visit, and treatment-by-visit interaction as factors and Baseline AAPS and Baseline value (if applicable) as covariates. Visit will include all scheduled visits except Visit 9 (Week 14). Least squares means, standard errors (SEs), and 95% confidence intervals (CIs) for the treatments and their difference will be presented together with the p-values.

Continuous endpoints derived from the eDiary (eg, score in abdominal pain, bloating, discomfort, number of bowel movements), will be analyzed using the MMRM above that includes scheduled visit, as well as a second MMRM model that includes treatment, the stratification factors, week, and treatment-by-week interaction as factors and Baseline AAPS and Baseline value (if applicable) as covariates. Week will include each week from Week 1 to Week 12. Least squares means, standard errors (SEs), and 95% confidence intervals (CIs) for the treatments and their difference will be presented together with the p-values.

Categorical endpoints will be analyzed by either the Cochran-Mantel-Haenszel (CMH) method, Fisher's exact test, or by logistic regression with a model that includes treatment and stratification factors as factors and Baseline AAPS and Baseline value (if applicable) as covariates. The odds ratio relative to placebo and percentage of difference from placebo will be presented together with corresponding 95% CIs and the p-values.

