#### **Exploratory**

## **8.3.1.2.** Long-Term Extension Endpoints

## **Primary**

## **8.3.2.** Main Study Efficacy Analyses

Statistical analysis methods for efficacy analyses in the Main Study are listed in Table 6.

**Table 6:** Statistical Analysis Methods for Efficacy Analyses

Endpoint	Statistical Analysis Methods
Primary	The primary endpoint, change in AAPS from Baseline to Week 12, will be analyzed using a MMRM analysis with treatment, stratification factors, visit, and treatment-by-visit interaction as factors and Baseline AAPS as a covariate. An unstructured variance-covariance matrix will be used for the MMRM analysis. Least squares means, SEs, and 95% CIs for the treatments and their difference will be presented together with the p-values.  The primary analysis will be conducted in the FAS. Sensitivity analyses will be detailed in the SAP.
Secondary	The proportion of subjects achieving a ≥ 30% improvement in AAPS from Baseline to Week 12 will be analyzed using the CMH test stratified by the stratification factors. The odds ratio relative to placebo and percentage of difference from placebo will be presented together with corresponding 95% CIs and the p-values.
	The proportion of subjects achieving a $\geq 30\%$ improvement in AAPS for at least 6 of the 12 weeks during the Treatment Period will be analyzed using the CMH test stratified by the stratification factors. The odds ratio relative to placebo and percentage of difference from placebo will be presented together with corresponding 95% CIs and the p-values.
	The percent change in AAPS from Baseline to Week 12 and Change from Baseline to Week 12 in number of pain free days will be analyzed using the same MMRM analysis as specified for the primary endpoint above.
	The change and percent change in AAPS from Baseline to Week 12 and change from Baseline to Week 12 in number of pain-free days per week will be analyzed using another MMRM model with treatment, stratification factors, week, and treatment-by-week interaction as factors and Baseline AAPS as a covariate. An unstructured variance-covariance matrix will be used for the MMRM analysis. Least squares means, SEs, and 95% CIs for the treatments and their difference will be presented together with the p-values.
	A detailed description of PK analyses will be provided in the SAP.
	Additional details regarding the statistical methods for secondary endpoints will be described in the SAP.

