#### 18.1.3. PRIMARY ANALYSIS OF PRIMARY EFFICACY VARIABLE

The primary efficacy analysis will be performed using the FAS population. The primary efficacy endpoint will be analyzed using a MMRM analysis with treatment group (placebo, olorinab 10 mg, olorinab 25 mg, olorinab 50 mg), stratification factors (sex and IBS subtype), week, and treatment-by-week interaction as factors and baseline AAPS as a covariate. Week will include each week from Week 1 to Week 12 based on eDiary data beginning from Day 1 (Randomization). In addition, two additional MMRMs will be completed with the following treatment groupings: 1) placebo, olorinab 10 mg, and olorinab 25 and 50 mg pooled and 2) placebo and pooled olorinab.

The primary objective of this study is to test the hypothesis that the change in AAPS from baseline to Week 12 is the same across treatment group (placebo, olorinab 10 mg, 25 mg, and 50 mg). The alternative hypothesis is that the change in AAPS from baseline to Week 12 differs between placebo and one of the olorinab treatments (10 mg, 25 mg, or 50 mg) or olorinab 25 mg/50 mg pooled.

Four hypothesis tests for the primary endpoint using the primary analysis methodology

described above are specified below.

- MMRM model with treatment groups (placebo, 10 mg, 25 mg, and 50 mg), and with
   3 pre-specified comparisons of placebo vs. the individual treatment groups of olorinab (10 mg, 25 mg, and 50 mg)
- MMRM with treatment "groups" placebo, 10 mg, and pooled olorinab [25 mg + 50 mg], and with 1 pre-specified comparison of placebo vs. the pooled olorinab group [25 mg + 50 mg]

No multiplicity control is planned for this Phase 2 study. If any of the four pre-specified hypothesis test analyses demonstrates statistical significance at the 0.05 (2-sided) significance level at Week 12, then the study successfully demonstrated that the primary endpoint was met.

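### SAP 4.3 reports no changes, but SAP 18.1.3 reverses the protocol's ranking of the two AAPS models and leaves two decision rules without an order

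*SAP*

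**What the plan says.** **Protocol.** The synopsis specifies for the primary endpoint a "mixed-effects model repeated measures (MMRM) analysis with treatment, stratification factors, visit, and treatment-by-visit interaction as factors and Baseline AAPS as a covariate". The Primary row of Table 6 (section 8.3.2) repeats that the endpoint "will be analyzed using a MMRM analysis with treatment, stratification factors, visit, and treatment-by-visit interaction as factors and Baseline AAPS as a covariate". The by-week model comes second. Section 8.3 plans the by-visit model for diary endpoints "as well as a second MMRM model that includes treatment, the stratification factors, week, and treatment-by-week interaction as factors", and the Secondary row of Table 6 says that change in AAPS, among other endpoints, "will be analyzed using another MMRM model with treatment, stratification factors, week, and treatment-by-week interaction as factors". Section 8.3 plans each dose against placebo and pooled olorinab against placebo; the pool sized in 8.1 is all three doses (180 subjects). Section 8.7 plans no testing strategy and treats the comparisons as exploratory.

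**Main Study SAP.** Section 4.3 says: "There are no changes in analysis or definitions from those planned in the final protocol". Section 18.1.3 then defines the primary model with "stratification factors (sex and IBS subtype), week, and treatment-by-week interaction as factors and baseline AAPS as a covariate" and calls the by-visit analysis supporting. It sets out "Four hypothesis tests for the primary endpoint using the primary analysis methodology": 10, 25 and 50 mg each against placebo, and 25 and 50 mg pooled against placebo. If any one of them reaches two-sided 0.05 at Week 12, "then the study successfully demonstrated that the primary endpoint was met". The by-visit paragraph adds that significance for one active dose in one of the MMRM models allows olorinab to be declared statistically better than placebo on AAPS reduction. Section 18.2.1 lists six responder endpoints as secondary; Protocol 8.3.1.1 lists two.

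**The concern.** The changes section is where a reader learns whether the reported primary analysis is the one the protocol planned. Anyone relying on 4.3 would take the by-week result for the protocol's primary analysis, when the protocol gave that place to the by-visit model.

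The second problem lies inside 18.1.3. One rule ties success on the primary endpoint to four by-week tests. The other allows a superiority statement from one of the MMRM models, and no order between the rules is given. That phrase may cover the by-visit models only or every MMRM; on either reading the by-visit model is enough. The report could then say that the primary endpoint was not met and also that olorinab was statistically better on the same variable at the same week.

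**Working it through.** **1. The plan's own figure.** With 60 per group, difference 1.0, SD 1.9 and two-sided 0.05 (Protocol 8.1, SAP 8), a two-sample t-test has 81.6% power, which agrees with the stated 80% or more. The calculation does not depend on which MMRM is primary, so it does not bear on this point.

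**2. The documents side by side.**

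| Item | Protocol | Main Study SAP |
|---|---|---|
| Primary model | by visit (synopsis; Table 6, Primary) | by week (18.1.3) |
| Other model | by week (8.3; Table 6, Secondary) | by visit, supporting (18.1.3) |
| Success rule | none visible; exploratory use (8.7) | any of four tests (18.1.3) |
| Pool | all three doses, 180 subjects (8.1) | 25 and 50 mg in the fourth test (18.1.3) |
| Responder endpoints listed as secondary | 2 (8.3.1.1) | 6 (18.2.1) |
| Changes declared | – | none (4.3) |

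**3. How often the two rules would disagree if no dose works.** This was simulated over 2,000,000 null trials with four equal arms and a shared placebo. Let X0 be the standardised placebo mean and X1, X2, X3 those for 10, 25 and 50 mg.

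- Dose contrast: Z = (Xi − X0)/√2
- Pooled 25 and 50 mg: Z = ((X2 + X3)/2 − X0)/√1.5
- All-dose pool: Z = ((X1 + X2 + X3)/3 − X0)/√(4/3)
- By-visit arm mean: ρX + √(1 − ρ²)E, with E independent standard normal

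A test counts when Z exceeds 1.96 in olorinab's favour. The correlation ρ between the two models' Week 12 estimates is an assumption.

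Within one model, the chance of at least one such result is 6.3% for the three dose contrasts and 6.5% for the SAP's four tests. It is also 6.5% for the three contrasts plus the protocol's all-dose pool.

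| At least one result in olorinab's favour | ρ = 0.98 | ρ = 0.95 | ρ = 0.90 |
|---|---|---|---|
| SAP: four by-week tests plus three by-visit dose contrasts | 7.5% | 8.1% | 8.8% |
| By-visit dose contrast significant, all four by-week tests miss | 1.0% | 1.6% | 2.3% |
| Protocol: three contrasts and all-dose pool, both models | 7.6% | 8.2% | 8.9% |

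At ρ = 1 the second row is zero. The first and third rows are almost equal: the comparisons that the protocol had already planned carry the same chance of a false favourable result. What the SAP adds is decision wording attached to such comparisons.

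**The case against.** The strongest reply is that little of substance moved. Both models were in the protocol, each with p-values. SAP 18.1.3 says openly which is primary and which is supporting, SAP 5.2 requires sign-off before lock and unblinding, and neither document plans type I error control. The by-visit model was the protocol's primary, so letting it support a statement could even be seen as preserving its role.

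Most of that stands and limits the point. It does not make 4.3 true: Table 6 fixes the primary model and leaves to the SAP only the sensitivity analyses and further secondary and PK detail. Nor does it order the two rules. If the by-visit model was meant to keep a deciding role, the SAP should not have tied the primary endpoint to by-week tests alone.

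A reader might infer more, and the documents do not support it:

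- **Inflated error.** Section 3 of the working shows no meaningful increase over the protocol's own set of comparisons, and no stated alpha exists to be breached.
- **A data-driven swap.** Nothing shows this, and SAP 5.2 points the other way.
- **A new AAPS definition.** Protocol 3.2 averages the 7 days before a visit and SAP 7.2 uses fixed weekly blocks, but the protocol's own by-week model needs weekly values.
- **New responder endpoints.** The protocol's exploratory list is not visible, so the 40% and 50% endpoints are at most a change of rank.
- **A changed PK set.** SAP 6.6 is narrower, but Protocol 8.3.3 leaves PK details to the SAP.

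**Conclusion.** SAP 4.3 is wrong as written. The ranking of the primary and second models is reversed without disclosure, and a success rule with a 25 and 50 mg pool appears that the visible protocol lacks. Both follow from the text alone.

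The by-visit sentence in 18.1.3 does not alter whether the primary endpoint is met. It does permit a superiority statement when all four by-week tests miss, in about 1.0% to 2.3% of null trials. That range rests on normal-theory tests, 60 per arm and an assumed correlation of 0.98 to 0.90. The problem is one of disclosure and of two unordered rules, in an exploratory Phase 2 study. It should be corrected, but it does not invalidate the analysis.

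**What to change.** SAP 4.3 for the long-term extension says that the Main Study analysis is complete, so the correction belongs in the study report, which is not among the documents and may already contain part of it.

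- In place of the no-changes statement, list with reasons the reversed model ranking, the any-of-four rule with its 25 and 50 mg pool, and the secondary listing of the 40% and 50% responder endpoints.
- Report both models and state that the protocol named by-visit as primary.
- Keep the ranking in the SAP; do not re-rank the models after unblinding.
- Base any superiority statement on the four by-week tests, with by-visit shown as supportive.
- Leave the signed SAP as it is. Date any note to file as post-unblinding.

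The cost is report wording. Both models are already planned in both documents, so no new analysis is needed.
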